2.2 Secondary objectives

To characterize REE, TEE, and ME following low-CHO, versus low-fat diet.

8. Trial design

The CHAMPION study was designed as a two-arm randomized clinical trial. Randomization (1:1) was performed using a computer-generated randomization scheme prepared with PROC PLAN in SAS Ver. 9.4.

Methods: Participants, interventions, and outcomes

9. Study setting

Data will be collected from healthy, but obese, AA women in the Birmingham, AL, metro area in The United States of America. Study testing will be performed in the Core facilities of the Center for Clinical and Translational Science (CCTS), Nutrition Obesity Research Center (NORC), and Diabetes Research Center (DRC) at UAB.

10. Eligibility criteria:

Participants will provide written, informed consent before the start of the study (see Appendix 1 for sample Informed Consent Form).

Inclusion criteria

Participants eligible for the study must comply with all of the following at randomization:

1. Age 19-65 years
2. African American female
3. BMI 30-45 kg/m²
4. Sedentary to moderately active
5. Normal menstrual cycle in premenopausal women
6. Normal glucose tolerance based on HbA1c less than 6.0%

Exclusion criteria

1. History of eating disorder
2. Daily use of tobacco (>1 pk/wk)
3. Change in weight greater than 5 lb in the previous 3 months
4. Presence of any condition (e.g. PCOS) or use of any medication (e.g., glucocorticoid) deemed by the project physician to interfere with study outcomes.

11a Interventions: description

Participants will be randomized to either low-fat or low-CHO hypocaloric diets for 10wks, followed by a 4-week weight stabilization period, with all food provided throughout.

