Strategies used to improve adherence to intervention protocols included weekly phone calls with participants to report previous week's specific food intake, report current body weight, and troubleshooting/support from a Registered Dietitian. Procedures for monitoring adherence include the measurement of respiratory quotient by indirect calorimetry, body weight and composition by bioelectrical Impedance Analysis and blood draw for the quantification of β -hydroxybutyrate, insulin, glucose, triglycerides, and cholesterol.

11d Interventions: concomitant care

Participants will be prohibited from participating in other weight loss programs (diet, exercise, and/or medications that induce weight loss). Participants will be instructed to continue their usual physical activity while in the study.

12. Outcomes

Main outcome measures: S_1 and AIR_g will be measured at baseline with an intravenous glucose tolerance test, body composition with bioimpedance at baseline and Wk10. REE and body composition will also be measured at week 5. REE, TEE, and mechanical efficiency (ME) will be measured with indirect calorimetry, doubly labeled water, and a submaximal bike test, respectively, at baseline and Wk14.

13. Participant timeline

Participants were enrolled between June 2019 and August 2023. Participants will complete 10 weeks of hypocaloric diet, 4 weeks of weight stabilization, and 6 months of weight loss maintenance. See figure 1.

[figure not shown]

Fig. 1 Schematic diagram of the study design.

14. Sample size

This study was powered for differences in FM loss between the two diet groups. Our published data indicate that AA (both men and women) lose more FM when consuming a LG vs HG diet over 16 weeks (1). Subgroup analysis within only the AA women (n=17), for only the 8-week hypocaloric phase, indicated that the women lost more FM with the LG diet [4.5 ± 1.0 (SEM) kg] vs the HG diet [2.0 ± 0.9 (SEM) kg] at a significance level of $P=0.113$. Based on these numbers, with 74 women (37/ group) we would have 80% power to detect a difference of 2.5 kg in FM loss between diets.

15. Recruitment

We will recruit from the local communities (UAB, city of Birmingham, and Jefferson and Shelby counties) via radio, newspaper, web-based advertisement, television advertisement, Research Match, UAB Reporter, word of mouth, and posting of flyers.

Methods: Assignment of interventions

16a Allocation: sequence generation

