After baseline testing, participants were randomized to one of two diets (low-glycemic, LG or high glycemic, HG) using a computer generated randomization scheme prepared with PROC PLAN in SAS Ver. 9.4.

16b Allocation concealment mechanism

Randomizations were placed in sealed sequentially numbered envelopes until interventions were assigned. All participants who give consent for participation, who fulfill the inclusion criteria, and complete baseline testing will be randomized. Participants will be enrolled by eligibility from the study team (principal investigator, coordinators, and dietitians). Study Coordinator will open sequentially numbered envelopes for diet intervention. The study dietitians will reveal the diet intervention to participants, along with a detailed diet introduction and explanation.

17a Blinding (masking)

No blinding. Since it was necessary to reveal the diet assignment to the study dietitian and the participant for appropriate diet introduction and education to the participant, this study will not involve blinding.

17b Blinding (masking): emergency unblinding

N/A

Methods: Data collection, management, and analysis

18a Data collection plan

All measurements will be done in the Core facilities of the Center for Clinical and Translational Science (CCTS), Nutrition Obesity Research Center (NORC), and Diabetes Research Center (DRC) at UAB. Participants will be instructed to avoid strenuous physical

activity (PA) the day prior to testing, and all PA on the morning of testing. All S_I tests will be performed in the Clinical Research Unit (CRU) at UAB's CCTS after an overnight fast of 12 h. The following measurements will be performed at baseline and end of weeks 10 and 14, unless otherwise stated.

S_I will be assessed at baseline only using the intravenous glucose tolerance test (IVGTT) and minimal modeling, as previously described (2), but using 300 mg of glucose (20 % dextrose)/kg of body weight. AIRg will be calculated as the incremental insulin area-under-the-curve from minutes 0–10 following glucose injection using the trapezoidal method.

Body composition (FM and fat-free mass) will be determined by bioimpedance analysis (BIA) (Seca 514 mBCA, Seca GmHb & Co. KG, Hamburg, Germany).

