All records pertaining to medical history, participation in this study, and data collected will be kept strictly confidential and will be recorded only by study number, to protect participant privacy. Only study investigators and the UAB IRB will have access to this data. Information regarding participant demographics, body composition, metabolic outcomes, or blood outcome measures will be shared and labeled with the study number, a unique identifier, and the date of acquisition.

20a Statistics: outcomes

Statistical analysis will be performed with SPSS version 29 (SPSS Inc., Chicago, IL), and data presented as mean \pm SD (or SEM). Statistical significance will be set at $P < 0.05$, unless otherwise specified, and normality of variables was assessed by visual inspection of histogram and Shapiro-Wilk test. Participants will be included in the analysis if they have S_I data at baseline, and body composition at baseline and week 10.

To test the hypothesis that AA women with obesity randomized to a low-CHO diet lose more FM than those randomized to a low-fat diet, we will analyze data from Phase 1 with generalized linear models (GLM). FM at week 10 will be the dependent variable, baseline FM, diet group, and S_I (and/or AIR) the covariates. Finally, to test the hypothesis that S_I (and/or) modulates the response to diet, a “diet \times S_I ” interaction term will be added to the models; i.e., $\Delta FM = \beta_0 + \beta_1 \text{ baseline FM} + \beta_2 \text{ baseline } S_I + \beta_3 \text{ diet group} + \beta_4 \text{ diet group} * S_I + e_1$.

To test the hypothesis that AA women with obesity randomized to a low-CHO diet maintain a higher TEE and REE, and a lower ME, than those randomized to a low-fat diet, we analyzed data from the end of Phase 2 with GLM. TEE, REE, or ME (week 14) were the dependent variables; baseline TEE, REE, or ME, diet group, and S_I (and/or AIRg) the covariates. For all

outcomes, we tested for a phenotype-by-diet interaction by adding relevant interaction terms to the model; e.g., $\Delta\text{TEE} (\text{week 14} - \text{baseline}) = \beta_0 + \beta_1 \text{baseline TEE} + \beta_2 \text{baseline S}_i + \beta_3 \text{diet group} + \beta_4 \text{diet group} * \text{S}_i + e_1$.

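### Section 20a makes baseline S_I a condition of every analysis, so a randomised woman without a usable S_I would be left out of the diet comparison even if her fat mass data are complete

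*Combined protocol and SAP*

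**What the plan says.** - **Sizing (Section 14).** "This study was powered for differences in FM loss between the two diet groups". The calculation uses FM loss and diet only, and S_I does not enter it.
- **Entry (Sections 10 and 16b).** The eligibility list has no S_I criterion. Section 16b states: "All participants who give consent for participation, who fulfill the inclusion criteria, and complete baseline testing will be randomized".
- **Source of S_I and AIRg (Section 18a).** S_I is measured at baseline only, from the IVGTT by minimal modelling. AIRg is a trapezoidal insulin area over the first 10 minutes of the same test.
- **Analysis set (Section 20a).** "Participants will be included in the analysis if they have S_I data at baseline", together with body composition at baseline and week 10. Section 20c, which should define the analysis population and missing-data handling, is marked not applicable.
- **Model (Section 20a).** For the diet hypothesis, week-10 FM is modelled on baseline FM, diet group and S_I and/or AIR. A diet-by-S_I term is then added.
- **Amendment (Sections 11b and 25).** The REE and exercise tests became optional and the week-14 IVGTT was dropped. The baseline IVGTT is not listed as optional.

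**The concern.** The entry rule and the analysis rule are not the same. Entry asks that baseline testing be completed. Analysis asks that one derived baseline quantity exist. S_I is the output of a model fitted to the test data, so a completed test and a usable S_I are different things, and the plan does not say what happens when the first occurs without the second.

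A woman in that position may have baseline FM, week-10 FM and a diet assignment, which is all the Section 14 contrast needs. As written, a missing covariate removes her. The same clause takes her out of the AIRg models, although AIRg needs no minimal model and may be valid when the S_I fit is not. AIRg stands beside S_I and diet in the primary objective (Section 2.1).

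At stake are some precision in the comparison that set the sample size and some breadth in the population it describes. There is also a point of conduct. Section 17a states that the trial is unblinded, and no section says when or by whom S_I usability is judged. A judgement made after allocation would be an avoidable discretionary exclusion.

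**Working it through.** **Step 1. Can the S_I clause exclude a randomised woman?**

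- Section 16b requires completed testing, which includes the IVGTT. A woman who never had the test should therefore not have been randomised.
- Completion cannot mean that every baseline value exists. Section 18a lists REE and the cycling test as baseline measures, and the amendment made both optional.
- Section 22 provides for stopping a test on discomfort and does not say what follows for randomisation.
- If entry did guarantee a usable S_I, the clause in 20a would have no effect.

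So the clause either excludes some randomised women or is redundant. The documents do not show which.

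**Step 2. Inputs.**

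- Section 14: "with 74 women (37/ group) we would have 80% power to detect a difference of 2.5 kg in FM loss between diets".
- Section 20a: "Statistical significance will be set at $P < 0.05$, unless otherwise specified". Sidedness is not stated; two-sided is assumed.
- Section 8: "Randomization (1:1) was performed using a computer-generated randomization scheme".
- Section 14, pilot: "the women lost more FM with the LG diet [4.5 ± 1.0 (SEM) kg] vs the HG diet [2.0 ± 0.9 (SEM) kg", from 17 women. The split by diet is not given; 8 and 9 is assumed.
- Number without S_I: not given. Losses of 1, 2 and 4 per arm are assumed (1/37 = 2.7%, 2/37 = 5.4%, 4/37 = 10.8%).

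**Step 3. The plan's own figure.** SD = SEM × √n gives 1.0 × √8 = 2.83 kg and 0.9 × √9 = 2.70 kg. The pooled SD is √[(7 × 8.00 + 8 × 7.29)/15] = √7.62 = 2.76 kg. At that SD, 80% power for 2.5 kg needs 21 per group by the t test, not 37. Over all splits from 3/14 to 14/3 the answer is 21 to 33. The stated 37 is not reproduced. That is a separate matter, but it means power must be shown at two SDs.

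**Step 4. SD implied by Section 14.** With n per group, the noncentrality is 2.5 / (SD × √(2/n)) on 2n − 2 degrees of freedom. For n = 37, 80% power requires a noncentrality of 2.84, so SD = 2.5 / (2.84 × √(2/37)) = 2.5 / (2.84 × 0.2325) = 3.79 kg.

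**Step 5. Power if women are lost through the S_I clause.**

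| Lost per arm | n per group | Noncentrality, SD 3.79 | Power | Noncentrality, SD 2.76 | Power |
|---|---|---|---|---|---|
| 0 | 37 | 2.84 | 80.0% | 3.90 | 97.0% |
| 1 | 36 | 2.80 | 78.9% | 3.84 | 96.6% |
| 2 | 35 | 2.76 | 77.7% | 3.79 | 96.2% |
| 4 | 33 | 2.68 | 75.2% | 3.68 | 95.2% |

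Whatever the SD, the standard error of the diet difference grows by √(37/n): 1.4%, 2.8% and 5.9% for losses of 1, 2 and 4.

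These are unadjusted two-group figures. The gain from adjusting for baseline FM cannot be computed from the documents.

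**The case against.** The strongest reply is that S_I belongs to the baseline testing that must be finished before randomisation, and that the amendment left the baseline IVGTT mandatory. On that view nobody is lost. This stands in part. It rules out women who skipped the test, but not a completed or terminated test that gives no usable value.

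A second reply is that the 20a model for the diet hypothesis lists S_I and/or AIR as a covariate, and that the primary analyses concern S_I together with diet. Requiring S_I follows from that model, and a common set keeps the main-effect and interaction models comparable. That is a real advantage. It is not a necessity: randomisation identifies the diet main effect without S_I, and a covariate measured before randomisation can be filled in without losing anyone.

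A third reply is that exclusion on a pre-randomisation value does not by itself unbalance the arms. That stands, and it is why the point is one of precision and generalisability.

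A reader might infer two stronger things. One is that randomised women have in fact been dropped; the documents report no such case and no count. The other is that the clause trims the low-S_I end, where Section 1.1 expects a larger diet effect. That would require S_I estimation to fail more often at low S_I, and nothing in the documents says so.

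**Conclusion.** The point holds conditionally. As written, 20a would remove a randomised woman with complete FM data from the diet comparison and the AIRg models if her S_I were unusable, and nothing in the plan prevents such a woman from being randomised. The number is unknown.

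If 1 to 4 women per arm were affected, the cost would be about 1 to 5 percentage points of power at the SD implied by Section 14, and under 2 points at the pilot-based SD. This rests on the assumed losses, a two-sided 5% test, and either taking the stated 80% at face value or assuming an 8/9 pilot split. The documents do not support a claim of bias between arms.

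The clause is worth correcting because the correction is cheap, not because the expected harm is large. The requirement for week-10 body composition, in the same sentence of 20a, is a post-randomisation condition and a separate matter.

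**What to change.** In Section 20a:

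1. Estimate the diet main effect in all randomised women with FM data, from week-10 FM on baseline FM and diet. Keep S_I as a covariate, with missing baseline values set to the overall mean and a missing-value indicator added.
2. Apply the condition of having baseline S_I only to the models that estimate S_I or diet-by-S_I effects, and a condition of having AIRg only to the AIRg models.
3. Report by arm how many women each condition removes. State whether a usable S_I was required before allocation, and when usability was judged.

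The cost is a wording change and slightly different numbers in the main-effect and interaction models, which should be reported. Section 13 gives enrolment as ending in August 2023, and parts of 20a are in the past tense. If data have already been analysed, the change should be labelled as made after the fact, with results on the 20a set shown alongside. Keeping these women restores 37 per group only if none lacks week-10 FM; Section 14 states no allowance for that.
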